Appendix C Criteria for Identifying Potentially Clinically Important Laboratory Values

Analyte	Conventional Unit	Low PCI Criteria	High PCI Criteria
Hematology (whole blood)	Cint		
Hemoglobin (Male)	g/dL	<11	>17
Hemoglobin (Female)	g/dL	<10	>17
Hematocrit (Both)	%	<30	>50
Leukocyte (White Blood Cell	$\times 10^3/\text{uL}$	≤2.8	≥15
Count)			
Neutrophils	$\times 10^3/\text{uL}$	≤1.5	No upper limit
Eosinophils	%	≥10%	No lower limit
Platelet Count	× 10 ³ /uL	≤75	≥700
Chemistry (serum or plasma)			
ALT (SGPT)	U/L	No lower limit	≥3 × ULN
AST (SGOT)	U/L	No lower limit	≥3 × ULN
Gamma-Glutamyl Transferase (GGT)	U/L	No lower limit	≥3 ULN
Lactate Dehydrogenase (LDH)	U/L	No lower limit	≥3 × ULN
Alkaline Phosphatase	U/L	No lower limit	≥3 × ULN
Total Bilirubin	mg/dL	No lower limit	≥1.5 ULN
СРК	mg/dL	No lower limit	≥3 ULN
BUN	mg/dL	No lower limit	≥30.0
Serum Creatinine	mg/dL	Not Applicable	>1.5 ULN
Sodium	mEq/L	≤125	≥155
Potassium	mEq/L	≤3.0	≥5.5
Calcium, total	mg/dL	<8.0	>11.0
Chloride	mEq/L	≤85	≥120
Phosphorous, inorganic	mg/dL	≤1.0 mg/dL	≥4.5 mg/dL
Magnesium	mEq/L	≤0.7 mEq/L	≥5.0 mEq/L
Uric acid	mg/dL	No lower limit	≥8.5
Albumin	g/dL	≤2.6	≥6.0
Total Protein	g/dL	≤5.0	≥10.0
Glucose (random)	mg/dL	≤45.1	≥115.0
HbA _{1c}	%	No lower limit	≥7%
Total Cholesterol, Fasting	mg/dL	No lower limit	≥240 mg/dL
Urinalysis			
Blood (occult blood)		Not Applicable	≥ Moderate
Protein			
Trotein	mg/dL	Not Applicable	≥100 mg/dL

Abbreviations: ALT (SGPT)=alanine aminotransferase (serum glutamic-pyruvic transaminase); AST (SGOT)=aspartate aminotransferase (serum glutamic-oxaloacetic transaminase); BUN=blood urea nitrogen; CPK=creatine phosphokinase; HbA_{1c}=glycosylated hemoglobin; PCI=potentially clinically important; ULN=upper limit of normal.

Sinus bradycardia ^c ≤50 bpm decrease of ≥15 bpm Supraventricular premature beat Ventricular premature beat Ventricular premature beat Supraventricular tachycardia Ventricular tachycardia Ventricular tachycardia Ventricular tachycardia Atrial fibrillation Atrial fibrillation Ist atrioventricular block Atrial flutter Atrial flutter Atrial flutter Ist atrioventricular block Arrial flutter PR ≥0.20 second increase of ≥0.05 second all not present - present Conduction Ist atrioventricular block Arrial flutter All not present - present All not present - present Block Pre-excitation syndrome Arrial flutter Arrial flutter Arrial flutter All not present - present Arrial flutter Arrial flutter All not present - present All not present - present Arrial flutter Arrial flutter All not present - present Arrial flutter All not present - present Arrial flutter Arrial flutter All not present - present Arrial flutter All not present - present Arrial flutter Arrial flutter All not present - present Arrial flutter Arrial flutter All not present - present Arrial flutter Arrial flutter All not present - present Arrial flutter Arrial flutter All not present - present Arrial flutter Arrial flutter All not present - present Arrial flutter Arrial flutter All not present - present Arrial flutter Arrial flutter All not present - present Arrial flutter All not present - present Arrial flutter All not present - present Arrial flutter Arrial flutter All not present - present Arrial flutter All not present - present Arrial flutter All not present - present Arrial flutter Arrial flutter All not present - present Arrial flutter Arrial flutt	Rhythm				
Supraventricular premature beat Ventricular premature beat Ventricular premature beat Ventricular premature beat Supraventricular tachycardia all not present - present		Sinus tachycardia ^b	≥120 bpm	increase of ≥15 bpm	
Premature beat Ventricular premature beat Supraventricular tachycardia all not present - present		Sinus bradycardia ^c	≤50 bpm	decrease of ≥15 bpm	
Supraventricular tachycardia Atrial fibrillation Adult on the present - present Atrial fibrillation All and present - present Acute or subacute Acute o		premature beat	all	not present - present	
tachycardia Ventricular tachycardia Ventricular tachycardia Atrial fibrillation Atrial fibrillation Atrial fibrillation Atrial fibrillation Ist atrioventricular block 2nd atrioventricular block 3rd atrioventricular block 4 all not present - present Block 3rd atrioventricular block 4 all not present - present Block 4 all not present - present Block Active block Aright bundle-branch block Bre-excitation syndrome Other intraventricular conduction block Infarction Acute or subacute			all	not present - present	
Atrial fibrillation all not present - present Atrial flutter all not present - present Conduction Ist atrioventricular block 2nd atrioventricular block 3rd atrioventricular block Left bundle-branch block Right bundle-branch block Pre-excitation syndrome Other intraventricular conduction block Infarction Acute or subacute Old all not present - present Old all not present - present increase of 0.02 second		tachycardia	all	not present - present	
Atrial flutter all not present - present Conduction Ist atrioventricular block 2nd atrioventricular block 3rd atrioventricular block Left bundle-branch block Right bundle-branch block Pre-excitation syndrome Other intraventricular conduction block Infarction Acute or subacute ST/T Morphological Myocardial Ischemia Symmetrical T-wave inversion Increase in QTc Acute or subacute Myocardial Ischemia Acute or subacute Amount of present - present Acute or subacute Acute or			all	not present - present	
Conduction Ist atrioventricular block PR ≥0.20 second increase of≥0.05 second 2nd atrioventricular block all not present - present		Atrial fibrillation	all	not present - present	
1st atrioventricular block PR ≥0.20 second increase of ≥0.05 second 2nd atrioventricular block all not present - present block block all not present - present Left bundle-branch block all not present - present Right bundle-branch block all not present - present Right bundle-branch block all not present - present Pre-excitation syndrome all not present - present Other intraventricular conduction block ORS ≥0.12 second increase of 0.02 second Infarction Acute or subacute all not present - present Old all not present - present ST/T Morphological ≥12 weeks post trial entry Myocardial Ischemia all not present - present Symmetrical T-wave inversion 2 2 2 2 2 2 2 2 3 3		Atrial flutter	all	not present - present	
$ \begin{array}{c ccccccccccccccccccccccccccccccccccc$	Conduction				

Appendix F Criteria for Potentially Clinically Important Vital Signs

Vital Sign Parameter	Unit	Criteria		
		Observed Value	And/Or	Change Relative to Baseline
Systolic blood pressure (supine or sitting)	mmHg	≥140	And	Increase of≥20
		≤70	And	Decrease of≥20
Diastolic blood pressure (supine or sitting)	mmHg	≥90	And	Increase of≥15
		≤50	And	Decrease of ≥15
Pulse (supine or sitting)	bpm	≥120	And	Increase of≥15
		≤50	And	Decrease of≥15
Weight	kg	Not Applicable		Increase of ≥7%
				Decrease of ≥7%

Appendix G Syncope Adverse Event Questions

- Was there a trigger?
 - Did the subject experience any strong emotion, pain, exercise etc. that may have triggered the syncope?
- Was there a prodrome?
 - Did the subject have pre-syncope symptoms such as feeling faint, dizzy, sick, visual disturbances and ringing in the ears (tinnitus)?
- Did the subject change color?
 - Did the subject have a pallor or blue color?
- Did the subject lose consciousness?
 - If so, how long did the unconsciousness last?
- Were there other symptoms associated with syncope such as nausea, sweating, feeling faint.
 - Did the subject experience bradycardia or tachycardia during the syncope?
- Does the subject/family have history of syncope?
- To rule out seizure please indicate the following:
 - Was there a convulsion?
 - Was there tongue biting?
 - Was there urinary incontinence?
- How long did the syncope take for full recovery?
- What is the possible underlying cause of the syncope?
 - In your judgment, do you consider the event of syncope to be situational, vasovagal, neural, orthostatic, or arrhythmic syncope?
- Does the subject require therapy for the syncope?
- What is the risk for further events?
- Will the subject be referred to a specialist for further investigation?
- In your judgment, do you consider that the adverse event of syncope may place the subject at safety risk if he/she continues to participate in the study?

Appendix H Somnolence Adverse Event Questions

- What is the probable cause for the somnolence?
- Is the subject on any concomitant medication that is known to produce somnolence?
- How soon does the subject experience somnolence after taking study medication?
- How often does the subject experience somnolence during the day?
- Does the subject need to take a nap with each episode of somnolence?
- Does the subject take several naps during the day?
- Does the subject go to bed late watching TV or playing video games?
- Does the subject have insomnia/nightmare during the night that prevents him/her from sleeping well?
- How many hours does the subject sleep at night?
- Is the somnolence interfering with concentration at school and other the daily activities?
- Has narcolepsy or other sleep disorder been ruled-out?
- In your opinion, does the subject require therapy/medication to alleviate the somnolence?
- In your judgment, do you consider that the adverse event of somnolence may place the subject at safety risk if he/she continues to participate in the study?

1 INTRODUCTION

This statistical analysis plan (SAP) addendum provides further details per the Food and Drug Administration (FDA) comments on the SAP (Version 3) of Study ACP-103-069 dated 29 July 2024 for IND 157863.

2 EFFICACY ANALYSES

Section 12.4 Multiple Comparisons / Multiplicity (Page 27):

In response to the FDA's comments, the hierarchical testing procedure has been reverted to the testing procedures outlined in the previous version of the SAP, dated December 22, 2022, which is consistent with the protocol.

A hierarchical testing procedure will be used to control the Type I error rate across the two treatment comparisons (pimavanserin high dose vs. placebo and pimavanserin low dose vs. placebo) for the primary endpoint. The hypotheses testing will be conducted in sequential order: 1. pimavanserin high dose versus placebo, 2. pimavanserin low dose versus placebo. If the first comparison fails to reach statistical significance at the 2-sided 0.05 level, the subsequent comparison will be declared as not statistically significant regardless of the associated nominal p-value. The study-wise Type I error rate will be maintained at the significance level of 0.05.

Section 13.1.2.2 Tipping Point Analyses (Page 32):

In response to the FDA's comments, the tipping point analyses have been updated to remove the limitation on the delta value, allowing it to exceed 100% until the conclusion of the primary analysis is overturned.

This sensitivity analysis of the tipping point analysis will be implemented for Full Analysis Set using delta adjustment imputation. This MNAR (missing not at random) sensitivity analysis is to departure from MAR (missing at random) assumption by progressively increasing the delta until conclusion from the primary analysis is overturned. The delta value is 0% to 100%, 200%,.... in 5% increments of the observed treatment difference between a pimavanserin high dose and placebo, pimavanserin low dose and placebo, from the primary analysis of MMRM (mixed model for repeated measures) model until conclusion of the primary analysis is overturned.

Signature Page for ACP-103-069 Statistical Analysis Plan Addendum

Approval w eSig Task	PPDPPDPPD
	14-Oct-2024 17:46:04 GMT+0000
Approval w eSig Task	PPD 1cs 14-Oct-2024 17:46:43 GMT+0000
Approval w eSig Task	PPD s 14-Oct-2024 18:47:45 GMT+0000

Signature Page for ACP-103-069 Statistical Analysis Plan Addendum

STATISTICAL ANALYSIS PLAN

Protocol No.:	ACP-103-069
Protocol Title:	A Phase 2, Randomized, Double-blind, Placebo-controlled Study to Evaluate the Efficacy and Safety of Pimavanserin for the Treatment of Irritability Associated With Autism Spectrum Disorder
Drug:	Pimavanserin

eGFR	estimated glomerular filtration rate
ESRS-A	Extrapyramidal Symptom Rating Scale–Abbreviated
ET	early termination
EOT	end of treatment
FAS	Full Analysis Set
FDA	Food and Drug Administration
GSD	Guidance for Site Documentation and Data Management Querying of Data Impacted by COVID-19
HbA _{1c}	glycosylated hemoglobin
HIV	human immunodeficiency virus
ICE	intercurrent event
IQ	intelligence quotient
MAR	missing at random
MedDRA	Medical Dictionary for Regulatory Activities
MI	multiple imputation

Terms	Definitions
MINI-KID	Mini International Neuropsychiatric Interview for Children and Adolescents
MMRM	mixed model for repeated measures
MNAR	missing not at random
Msec	milliseconds
PCI	potentially clinically important
PD	pharmacodynamic
PK	pharmacokinetic
QRS	QRS interval of ECG
QT	QT interval for heart rate of ECG
QTc	corrected QT interval of ECG for heart rate
QTcB	corrected QT interval using Bazett's correction method
QTcF	QT interval corrected for heart rate using Fridericia's formula
RBS-R	Repetitive Behavior Scale–Revised
SAE	serious adverse event
SAP	statistical analysis plan
SD	standard deviation
SE	standard error
SOC	system organ class
TEAE	treatment-emergent adverse event
ULN	upper limit of normal
US	United States
VABS	Vineland Adaptive Behavior Scales

1 INTRODUCTION

This statistical analysis plan (SAP) provides a technical and detailed elaboration of the statistical analyses of efficacy and safety data based on the study protocol Amendment 4.0 dated 21 December 2022, and the electronic case report form (eCRF). The SAP will be finalized and approved before database lock of the final analysis.

For Italy, a country-specific protocol amendment (Amendment 4-IT finalized 12 July 2023) added the details of the Schwartz equation and modified the exclusion criterion #23 to also exclude patients whose estimated glomerular filtration rate (eGFR) is <30 mL/min as calculated by the bedside Schwartz equation.

Specifications for tables, figures, and listings will be provided in a separate document. Statistical analyses for population pharmacokinetic (PK) and PK/pharmacodynamics (PD) modeling will be presented in a separate report and therefore will not be included in this SAP.

2 OBJECTIVES

2.1 Primary Objective

To evaluate the efficacy of pimavanserin compared with placebo in the treatment of irritability associated with Autism Spectrum Disorder (ASD) in children and adolescents.

2.2 Secondary Objective

To evaluate the efficacy of pimavanserin compared with placebo, in the treatment of non-irritability symptoms, the magnitude of improvement in irritability, and the response rate, in children and adolescents with ASD.

3 STUDY DESIGN

3.1 General Study Design

This study will be conducted as a 6-week, randomized, double-blind, fixed-dose, placebo-controlled, parallel group study in children and adolescents (5 through 17 years of age) with irritability, agitation, or self-injurious behaviors associated to ASD. Approximately 60 global sites and eight countries will participate in this study.

The study will have three periods:

[figure not shown]
• Screening period: 3-28 days

• Double-blind treatment period: 6 weeks

• Safety follow-up period: 30 (+3) days for those subjects who discontinue prematurely from the study or who do not enroll in the 52-week, open-label extension study (Study ACP-103-070)

The study design schematic is provided in Figure 1.

Figure 1 Schematic of Study Design

Abbreviations: ASD=autism spectrum disorder; EOT=end of treatment; ET=early termination; yrs=years

Subjects who complete the 6-week Treatment Period may be eligible to enroll in a 52-week, open-label extension study (Study ACP-103-070). Subjects entering ACP-103-070 will not complete a follow-up telephone call as they will be immediately enrolled in ACP-103-070.

3.2 Schedule of Assessments

The schedule of events and assessments for the study is presented in Appendix 21.1.

3.3 Randomization

Eligible subjects will be randomized in a 1:1:1 ratio to pimavanserin low dose, pimavanserin high dose, or placebo using an interactive response technology (IRT) system. The randomization will be stratified by age group (5- through 12-year-olds or 13- through 17-year-olds) and region (U.S. or rest of world). For the 5- through 12-year-olds, the subjects who are randomized to the low dose group will receive 10 mg/day pimavanserin and the subjects who are randomized to the high dose group will receive 20 mg/day pimavanserin. For the 13- through 17-year-olds, the subjects who are randomized to the low dose group will receive 20 mg/day pimavanserin and the subjects who are randomized to the high dose group will receive 34 mg/day pimavanserin. The assignments will be based on a pre-generated permuted-block randomization schedule.

3.4 Blinding

This is a double-blind study. Blinding will be assured by restricting access of Investigators and Sponsor personnel and/or designee to the treatment codes and providing identical capsules and packaging for the adjunctive pimavanserin and adjunctive placebo treatments. Neither the subjects nor the study personnel at the clinical sites will know which treatment is administered to each subject.

3.5 Determination of Sample Size

The planned sample size is a total of 228 subjects for both age groups combined (76 subjects randomized to each of the three treatment groups of equal sample sizes: pimavanserin high dose group, pimavanserin low dose group, and the placebo group). The total study sample size will be comprised of at least 35% (80) subjects in the younger age group (5- through 12-year-olds).

Assuming the true difference in the mean change in the ABC-Irritability (ABC-I) subscale score from Baseline at Week 6 is 5 points between each pimavanserin dose group and the placebo group, and assuming the common standard deviation is 10 points, 64 evaluable subjects per treatment group will provide 80% power to detect the difference between either pimavanserin dose group and the placebo group at a significance level of 0.05, using a 2-sided t-test. Adjusting for a potential discontinuation rate of up to 15%, approximately 76 subjects per treatment group, or 228 total subjects, will be randomized.

3.6 Coronavirus Disease 2019

In the context of the global COVID-19 pandemic or other natural disaster, the mechanisms to record information on the potential impact of the COVID-19 pandemic on data itself, as well as data collection and integrity, will be implemented. The impact of COVID-19 on the statistical analysis is discussed in each of the relevant sections of this SAP.

4 ANALYSIS SETS

Randomized Analysis Set

The Randomized Analysis Set will include all unique subjects who were randomized. Subjects will be analyzed based on their randomized treatment.

Safety Analysis Set

The Safety Analysis Set will include all randomized subjects who received at least one dose of study drug (pimavanserin or placebo). Subjects will be analyzed based on the treatment that they actually received. If a subject received wrong kit, the actual treatment group will be determined based on the majority of treatment the subject received. The Safety Analysis Set will be used for all safety analyses.

Full Analysis Set

The Full Analysis Set will include all randomized subjects who received at least one dose of study drug and who have both a baseline value and at least one post-baseline value for the ABC-I subscale score. Subjects will be analyzed based on their randomized treatment. The Full Analysis Set will be used for the analysis of all efficacy endpoints.

Pharmacokinetics Analysis Set

The Pharmacokinetics Analysis Set will include subjects in the Safety Analysis Set with at least one measurable plasma concentration. The Pharmacokinetics Analysis Set will be used for pimavanserin and AC-279 plasma concentration summaries.

5 GENERAL CONSIDERATIONS FOR DATA ANALYSES

5.1 Data Presentation Conventions

For continuous variables, the following summary statistics will be provided: number of subjects, mean, standard error of the mean (SE), standard deviation (SD), minimum, maximum, and median. Unless specified otherwise, means, medians, and confidence intervals (CIs) will be presented to one more decimal place than the raw data, and the SDs and SEs will be presented to 2 more decimal places than the raw data. Unless otherwise specified, the maximum number of

decimal places is 4 and values will be truncated to 4 decimal places in situations where there are more than 4 decimal places. Wherever possible data will be decimal aligned.

For categorical variables, summaries will include the number and percentage of subjects in each category. For demographic and baseline characteristics, the number of subjects and the percentage of subjects with missing data will be summarized (if applicable), and the denominator for percentages will be the total number of subjects in the given treatment group, unless otherwise specified. Categories with zero counts will not have zero percentages displayed. Percentages will be presented to 1 decimal place.

All data captured in the Electronic Data Capture (EDC) system will be presented in the listings.

Unless specified otherwise, all statistical tests will be 2-sided hypothesis tests performed at the significance level of 0.05 for main effects and all confidence intervals (CIs) will be 2-sided 95% CIs. P-values will generally be presented to 4 decimal places; values less than 0.0001 will be presented as <0.0001.

Values that are collected with "<" or ">" signs will generally be analysed as the numerical value without the sign in tables and figures. In listings, these data will be reported as collected with the sign.

Duration in years is calculated as number of days/365.25 and will be rounded to 1 digit after the decimal point (tenths) for presentation purposes.

Duration in months is calculated as (number of days/365.25)×12 and will be rounded to 1 digit after the decimal point (tenths) for presentation purposes.

5.2 Derived Variables

In general, the assessment scale total scores and subscores will be derived within the analysis datasets, if those scores are not automatically generated in EDC. In the event that total scores and/or subscores are also collected on the eCRF, the derived values will be used for all analyses. Both the raw and derived scores will be presented in the listings.

5.2.1 Aberrant Behavior Checklist

The Aberrant Behavior Checklist (ABC) is a parent/caregiver-rated scale comprised of five empirically-derived subscales encompassing 58 items that describe various behavior problems (Aman et al. 1985; Kaat et al. 2014). The subscales have been labeled:

- I. Irritability (irritability, agitation, and crying) (15 items)
- II. Lethargy (lethargy and social withdrawal) (16 items)
- III. Stereotypic Behavior (7 items)

- IV. Hyperactivity (hyperactivity and noncompliance) (16 items)
- V. Inappropriate Speech (4 items)

The ABC will be administered at Screening and Baseline, and at all post-baseline visits from Week 1 through Week 6. Items are rated on a 4-point Likert scale ranging from 0 (not at all a problem) to 3 (the problem is severe), with higher scores indicating more severe problems. Subscale scores are calculated by summing the items within that subscale.

Missing ABC item scores will not be imputed. If any item is missing within a subscale, then that particular subscale score will be missing.

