12.1 Efficacy Variables

Primary Efficacy Endpoint

The primary efficacy endpoint is the change from Baseline at Week 6 in the ABC-I score.

Secondary Efficacy Endpoints

The secondary efficacy endpoints are the following:

- Change from Baseline at Week 6 in the caregiver-rated ABC subscale scores
 - o Stereotypic behavior
 - o Lethargy
 - Hyperactivity
 - o Inappropriate speech
- Change from Baseline at Week 6 in the Clinical Global Impression–Severity (CGI-S) of irritability score
- Clinical Global Impression–Improvement (CGI-I) of irritability score at Week 6
- Change from Baseline at Week 6 in the Repetitive Behavior Scale–Revised (RBS-R) scores
- Change from Baseline at Week 6 in the Vineland Adaptive Behavior Scales (VABS)—Socialization subscale score
- Change from Baseline at Week 6 in the Caregiver Strain Questionnaire (CGSQ) Since last visit scores
- Proportion of subjects who have at least 25% reduction from Baseline in the ABC Irritability subscale score at Week 6
- Proportion of subjects who have CGI-I of irritability score of 1 (very much improved) or 2 (much improved) at Week 6 (CGI-I of irritability responders)
- Proportion of subjects who have at least 25% reduction from Baseline in the ABC Irritability subscale score AND a CGI-I of irritability score of 1 (very much improved) or 2 (much improved) at Week 6

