13.2 Secondary and Exploratory Efficacy Analyses

The change from Baseline at each post-baseline timepoint in the ABC subscale scores (lethargy, stereotypic behavior, hyperactivity, inappropriate speech), the CGI-S of irritability score and the CGI-I of irritability score will be analyzed using an MMRM model similar to the primary analysis described above for the primary endpoint, except that the Baseline covariate of the endpoint being analyzed will be included in the model instead of the Baseline ABC-I subscale score. For CGI-I of irritability score, the Baseline covariate include in the MMRM model will be the Baseline CGI-S of irritability score

The change from Baseline at each post-baseline timepoint in the RBS-R scores, the VABS-Socialization subscale score, and the CGSQ scores will be analyzed using an MMRM model similar to the primary analysis described above for the primary endpoint, except that the Baseline value of the endpoint being analyzed will be included in the model instead of the Baseline ABC-I subscale score, also the visit variable included in the model will reflect the visits scheduled for the respective endpoints.

The proportion of subjects with ≥25% reduction in the ABC-I subscale score, the proportion of subjects with a CGI-I of irritability score of 1 or 2, and the proportion of subjects with ≥25% reduction in the ABC-I subscale score and a CGI-I of irritability score of 1 or 2 will be summarized at each post-Baseline timepoint. The proportions will be compared between each pimavanserin dose group and the placebo group using Cochran-Mantel-Haenszel test stratified by age group and region; Newcombe's 95% CI stratified by age group and region will be presented. Subjects with missing score at a given visit are considered as non-responders for that visit.

In addition to the treatment comparisons for the Week 6 timepoint, the treatment groups will also be compared at each of the other timepoints (Weeks 1, 2, 3, 4, or 5). These comparisons will be considered exploratory.

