21.4 Summary of Version Changes

Version	Document History	Author(s)	Version Date
No:	Description of Update		
1.0	Original version	[name]	30 APR 2021
1.1	Updated due to protocol amendments 1 and 2	[name]	10 DEC 2021
2.0	Updated due to protocol amendment 3 and FDA request to include SAS code for tipping point analysis	[name]	12 APR 2022
2.1	Reference Protocol Amendment 4	[name]	22 DEC 2022
3.0	Updated for changes in protocol amendment 4-IT; Removed the upper limit of Week 6 analysis visit window; Removed subgroup analysis by ADI-R and added subgroup analysis by stimulant use; Added details for some scales; Updated example SAS codes for sensitivity analysis and PCI cutoff for phosphate and urinalysis; Updated responder analysis to set missing score as non-responder; Updated hierarchical testing by adding the CGI-S; Added a section of Syncope and somnolence; Fixed minor typographical errors	[name]	29 JUL 2024

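### A blank ABC-Irritability item makes the score missing, and the responder rule then counts the child as a non-responder even when the answered items prove response

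*SAP*

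**What the plan says.** ABC-I has 15 items scored 0 to 3 (SAP 5.2.1). On scoring: "Subscale scores are calculated by summing the items within that subscale". On blanks: "Missing ABC item scores will not be imputed", and "If any item is missing within a subscale, then that particular subscale score will be missing". No number of answered items is treated as enough, and there is no proration.

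SAP 12.1 lists three responder endpoints at Week 6: at least a 25% reduction in ABC-I, CGI-I of 1 or 2, and both together. For these, SAP 13.2 states: "Subjects with missing score at a given visit are considered as non-responders for that visit". It makes no exception for a partly completed form. The rule was a deliberate change in SAP version 3.0; the version table in SAP 21.4 records "Updated responder analysis to set missing score as non-responder".

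The SAP addendum changes only the multiplicity procedure and the tipping-point analysis, so both rules stand. For the primary endpoint, SAP 12.3 leaves a missing ABC-I score unimputed and analyses the observed scores by MMRM under missing at random.

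**The concern.** Treating missing as non-response is a convention for outcomes that are not known. A form with one blank item is different. Each item scores 0 to 3, so the total is known to within 3 points, and for many forms every possible total falls on the same side of the 25% threshold. The two rules, read in sequence, ignore this. They record failure where the data show success, so a form-filling slip counts as a treatment outcome.

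What is at stake is the accuracy of two of the three responder rates. Equal loss across arms pulls both rates and their difference toward zero. Unequal loss could distort the difference in either direction.

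**Working it through.** **Inputs.** Fifteen items, each 0 to 3, plain sum (SAP 5.2.1). Response means a score of at most 0.75 × Baseline (SAP 12.1). Minimum Baseline 18 (Protocol 4.1, inclusion 8). 64 evaluable and 76 randomized per arm (SAP 3.5). The item-blank rate is in neither document, so every rate below is an assumption.

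**The plan's own figure.** For 5 points, SD 10, two-sided 0.05 and 80% power, the exact t-test gives 79.5% at 63 per arm and 80.1% at 64. Then 64 / 0.85 = 75.3, rounded up to 76, and 3 × 76 = 228. The stated numbers reproduce.

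**The bound.** Let S be the sum of the answered items and k the number blank. The true score lies between S and S + 3k. Response is certain if S + 3k ≤ 0.75 × Baseline, and non-response is certain if S > 0.75 × Baseline. With one blank:

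| Baseline | 0.75 × Baseline | Response certain if S ≤ | Undetermined S | Non-response certain if S ≥ |
|---|---|---|---|---|
| 18 | 13.5 | 10 | 11–13 | 14 |
| 25 | 18.75 | 15 | 16–18 | 19 |
| 28 | 21 | 18 | 19–21 | 22 |
| 30 | 22.5 | 19 | 20–22 | 23 |
| 40 | 30 | 27 | 28–30 | 31 |

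*Example.* Baseline 28, S = 10, one blank. The true score is 10 to 13, so the reduction is between (28 − 13)/28 = 54% and (28 − 10)/28 = 64%. The SAP codes non-response.

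**How often one blank still leaves response provable.** In a simulation with assumed Baseline mean 27 and SD 6 (limited to 18–45), mean change −8 or −13 with SD 10, and a blank unrelated to outcome, 87.5% and 91.9% of true responders with one blank item were provable responders. No non-responder was ever classed as a responder, as the bound guarantees.

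**How many scores could be lost.** With independent blanks at rate q per item, the share lost per visit is 1 − (1 − q)^15:

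| q (assumed) | Scores lost | Of 64 per arm |
|---|---|---|
| 0.1% | 1.5% | 1.0 |
| 0.5% | 7.2% | 4.6 |
| 1% | 14.0% | 9.0 |

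**Effect on a responder comparison.** If a share m is lost equally in all arms, regardless of outcome, each rate and the difference are multiplied by (1 − m). Take assumed rates of 35% and 55% and m = 5%: 0.35 × 0.95 = 33.25%, 0.55 × 0.95 = 52.25%, and the difference falls from 20.0 to 19.0 points. Power of a simple two-proportion comparison at 76 per arm falls from 70% to 66%.

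**Ceiling on the primary loss.** If lost Week 6 scores were dropped with nothing recovered from other visits, 64 × (1 − m) per arm at the three rates above would give power of 79.5%, 77.1% and 73.9%, against 80.1%. The MMRM uses the child's other visits, so the real loss should be smaller.

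**The case against.** Both rules are clear, deliberate and consistent with each other. Complete-item scoring is a legitimate choice, and so is counting missing as non-response. The affected endpoints are secondary: the addendum confines the hierarchy to the two primary comparisons, and SAP 12.4 already disclaimed inference for secondary endpoints other than CGI-S. With equal blanks across arms the effect is toward no difference, and nothing in the documents suggests unequal blanks.

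The documents also point to few blanks. Caregivers are trained before completing the ABC (Protocol 6), a clinician is available to help (Protocol 6.2.1), and eCRF omissions must be explained (Protocol 10.3). Blanks that cluster within forms would make the independence formula overstate the share of scores lost. Another complete ABC in the same window can supply the value (SAP 5.3.3 and 5.3.4). For the composite, the blank matters only when CGI-I is 1 or 2.

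All of this stands, and it limits the size and importance of the point. It does not remove it: none of these provisions guarantees a complete form, and where one is incomplete and unreplaced, the rules can assign an outcome that the recorded data contradict.

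**Conclusion.** The misclassification follows from the text by arithmetic and needs no assumption. It affects the ABC-I responder endpoint, and the composite when CGI-I is 1 or 2; the CGI-I responder endpoint is untouched. Its frequency is unknown. The range of 1.5% to 14% of scores per visit rests wholly on assumed independent blank rates of 0.1% to 1% per item, and the plan's safeguards may keep the true figure low. This is a modest correction to secondary endpoints.

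A reader might infer three stronger things that the documents do not support:

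- *The whole ABC form is thrown away.* Only the subscale containing the blank goes missing (SAP 5.2.1).
- *The primary analysis counts these children as failures.* The MMRM loses that visit's ABC-I score, keeps the child's other visits and assigns no failure (SAP 12.3, 13.1.1).
- *The primary scoring rule must therefore change.* Complete-item scoring is a stated choice. Proration would replace it with an assumption that the blank item resembles the others, and no cut-off for it appears in the documents.

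**What to change.** Add to SAP 13.2, before unblinding: when the Baseline ABC-I is complete and the analysis window holds no other complete ABC-I, count the ABC-I criterion as met if S + 3 × (number of blank ABC-I items) ≤ 0.75 × Baseline. Otherwise keep missing as non-response. Use the same result for the ABC-I part of the composite. Report incomplete ABC-I forms by arm and visit, with the number reclassified.

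The cost is a sentence or two in the SAP and a few lines of derivation code working from item scores. The rule needs no assumption about the blank item and cannot create a false responder. It is one-sided: undetermined forms stay non-responders, so a small shortfall remains. Sample size does not change.

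Leave the primary MMRM scoring rule as it is. Proration is at most an optional sensitivity analysis, and it can disagree with the bound. At Baseline 18, 14 items summing to 11 prorate to 11 × 15/14 = 11.8, a 35% reduction, yet the bound gives 11 + 3 = 14, above 13.5, so response is not proven.
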